2.2.1 Subgroup of interest

Subgroup analyses will be only performed in well-differentiated NET group.

Efficacy

The overall response rate will be summarized by the following subgroups to examine the homogeneity of treatment effect provided that the study meets the pre-specified criteria for primary efficacy based on the FAS:

- Cohort
- Sex
- Race
- PD-L1 expression with analyses for the following thresholds:
 - <1% vs $\geq 1\%$
 - <5% vs $\geq 5\%$
 - <10% vs $\geq 10\%$
 - <50% vs $\geq 50\%$
- Age category (< 65 years, ≥ 65 years)
- Tumor grade
- ECOG PS
- Occurrence of at least one immune-related AE (yes, no)

Summary tables will only be produced if sufficient number of patients is present in each subgroup. Only the point estimate of the overall response rate and 95%-confidence intervals will be provided (see [Sections 2.5](#) for further analysis details). The objective of the efficacy subgroup analysis is to demonstrate homogeneity of treatment effect in the above subgroups.

Safety

Safety subgroup analyses will use the same method as for the analysis in the overall analysis set. Key safety analyses (deaths, SAEs, AESIs, AEs leading to discontinuations) will be repeated on safety set in the following subgroups:

- Cohort
- Age group (< 65 years, ≥ 65 years)
- Sex
- Race
- Ethnicity

The objective for carrying out these subgroup analyses is to identify potential safety issues that may be limited to a subgroup of patients, or safety issues that are more commonly observed in a subgroup of patients.

Summary tables will only be produced if sufficient number of patients is present in each subgroup. Some grouping of classes will be considered for race and ethnicity.

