4.1 Description of study design

This is a phase II, single-arm, open-label, multi-center study in patients with

- Well-differentiated, non-functional, grade 1 or 2, neuroendocrine tumors of pancreatic, GI or thoracic (including lung and thymus) origins and
- Poorly-differentiated GEP-NEC

All patients must have progressed on or after the last treatment. (as described in [Section 5.1](#)).

A total of approximately 90 patients will be enrolled in the well-differentiated group, with approximately 30 patients enrolled in each cohort based on tumor origin. Approximately 20 patients will be enrolled in the poorly-differentiated GEP-NEC group, for a total number of approximately 110 patients.

Treatment duration

[figure not shown]
Patients will receive PDR001 at the dose of 400 mg Q4 weeks at flat dosing. Patients will continue to receive the assigned study treatment until disease progression by RECIST 1.1 or as per irRECIST (see below), unacceptable toxicity, start of a new anti-neoplastic therapy, withdrawal of consent, physician's decision, lost to follow-up, death or the study is terminated by the sponsor.

Patients may continue study treatment beyond disease progression by RECIST 1.1 until disease progression as per irRECIST, as per BIRC (if criteria stipulated in [Section 6.1.5.1](#) are fulfilled), unacceptable toxicity, start of new anti-neoplastic therapy, withdrawal of consent, physician's decision, lost to follow-up, death, or the study is terminated by the sponsor. In case of continuation of study treatment beyond disease progression by RECIST 1.1, the patient will continue assessments as defined in [Section 7](#). While the investigator is waiting for the results from the central imaging vendor confirming disease progression, the patient should continue on study treatment. However, during this time, the investigator should do whatever is medically necessary for his/her patient.

After the primary analysis cut-off date (10-Aug-2018):

- Response assessments by BIRC will no longer be performed.

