6.1.5.1 Treatment beyond disease progression

Emerging clinical data indicate that patients may derive benefit from continuing study treatment despite initial evidence of disease progression ([Section 2.5](#)).

Prior to the primary analysis cut-off date (10-Aug-2018), patients treated with PDR001 will be permitted to continue study treatment beyond initial disease progression as per RECIST 1.1 until disease progression per irRECIST, as per BIRC, unacceptable toxicity, start of new anti-neoplastic therapy provided they meet all of the following criteria:

- Absence of disease progression per irRECIST, as per BIRC, confirmed by 2 consecutive assessments
- The continuation of treatment beyond progression will not delay an imminent intervention to prevent serious complications of disease progression
- Patients exhibit adequate tolerance to study treatment
- Patient performance status is stable

Patients who meet the above criteria should continue study treatment beyond initial disease progression per RECIST 1.1 and continue all study procedures as outlined in [Section 7](#). The reasons for the patient continuing treatment will be documented in the eCRF.

In case of clinical deterioration or suspicion of disease progression, a follow-up imaging assessment should be performed promptly rather than waiting for the next scheduled assessment. Treatment with PDR001 in patients who are no longer deriving clinical benefit or have disease progression as per irRECIST by BIRC confirmed by 2 consecutive assessments must be discontinued.

After the primary analysis cut-off date (10-Aug-2018):

- Response assessments by BIRC will no longer be performed.
- Patients, who are on treatment but have not yet progressed per local tumor response assessment, will continue study treatment until documentation of disease progression by RECIST 1.1 as per local investigator assessment, unacceptable toxicity, start of new anti-neoplastic therapy, withdrawal of consent, physician's decision, subject/guardian decision, lost to follow-up, death or the study is terminated by the sponsor. These patients will be permitted to continue study treatment beyond initial PD as per RECIST 1.1 until confirmed irPD per local assessment (until 2 consecutive irPDs) provided they meet all of the following criteria:
 - Absence of disease progression per irRECIST, confirmed by 2 consecutive assessments

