For safety and efficacy evaluations, the last available assessment on or before the date of start of study treatment is defined as “baseline” assessment.

If patients have no value as defined above, the baseline result will be missing.

On-treatment assessment/event and observation periods

For adverse event reporting the overall observation period will be divided into three mutually exclusive segments:

1. ***pre-treatment period***: from day of patient’s informed consent to the day before first administration of study treatment
2. ***on-treatment period***: from date of first administration of study treatment to 30 days after date of last actual administration of any study treatment (including start and stop date)
3. ***post-treatment period***: starting at day 31 after last administration of study treatment.

Safety summaries (tables, figures) include only data from the on-treatment period with the exception of baseline data which will also be summarized where appropriate (e.g. change from baseline summaries). In addition, a separate summary for death including on treatment and post treatment deaths will be provided. In particular, summary tables for adverse events (AEs) will summarize only on-treatment events, with a start date during the on-treatment period (***treatment-emergent*** AEs).

Additional summaries will be displayed to report deaths, all AEs, AEs related to study treatment, all SAEs and SAEs related to study treatment collected up to 150 days after last administration of PDR001.

However, all safety data (including those from the post-treatment period) will be listed and those collected during the pre-treatment and post-treatment period will be flagged.

Last contact date

The last contact date will be derived for patients not known to have died at the analysis cut-off using the last complete date among the following:

Table 2-1 Last contact date data sources

Source data	Conditions
Last contact date/last date patient was known to be alive from Survival Follow-up page	- Patient status is reported to be alive, lost to follow-up or unknown.
Start/End dates from further antineoplastic therapy	Non-missing medication/procedure term.
Start/End* dates from drug administration record	Non-missing dose. Doses of 0 are allowed.
End of treatment date from end of treatment page	No condition.
Tumor (RECIST/irRECIST) assessment date	Evaluation is marked as 'done'.

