2.5.4 Supportive analyses

A sensitivity analysis considering patients with unconfirmed PR or CR (i.e. with PR or CR at the last assessment prior to the cutoff and ongoing in efficacy follow-up) as responders may be performed if large delayed treatment effect is observed.

The analysis of ORR will be repeated based on local review.

Concordance analysis of BOR

An assessment of the concordance between BIRC assessment and local assessment of the Best Overall Response for each subject will be provided. The calculation will be based on the percent agreement (the proportion of response outcomes that agree or match across both Independent Reviewer and Investigator Assessments):

Percent Agreement = (Number of matched responders + Number of matched non-responders) / total number of subjects assessed.

Subgroup analyses for the primary endpoint

If both criteria for the primary efficacy analysis are met, the primary endpoint of ORR will be summarized for the subgroups specified in [Section 2.2.1](#) based on the primary analysis source (i.e. BIRC) and the same conventions as for the primary analysis.

For each of the subgroups, the following analyses will be performed:

- Proportion of patients with objective response
- two-sided exact 95% CI

Efficacy analyses in subgroups will be purely exploratory and are intended to explore the consistency of treatment effect.

Reasons for “Unknown” BOR

Patients with ‘unknown’ BOR will be summarized by reason for having unknown status. The following reasons will be used:

- No valid post-baseline assessment
- All post-baseline assessments have overall lesion response UNK
- New anti-neoplastic therapy started before first post-baseline assessment
- SD or non-CR/non-PD too early
- PD too late

Note 1: A SD or Non-CR/Non-PD is considered as “SD too early” if the SD or Non-CR/Non-PD is documented within first 6 weeks after treatment start date.

Note 2: A PD is considered as “PD too late” if the first documentation of PD is recorded more than 12 weeks after treatment start date with no qualifying CR, PR or SD or Non-CR/Non-PD in between.

Note 3: Special (and rare) cases where BOR is “unknown” due to both too early SD and too late PD will be classified as “SD too early”.

Waterfall plot to depict anti-tumor activity

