2.8.1.1 Adverse events of special interest / grouping of AEs

Data analysis of AESIs

An adverse event of special interest (AESI) is a grouping of adverse events that are of scientific and medical concern specific to compound PDR001. These groupings are defined using MedDRA terms, SMQs (standardized MedDRA queries), HGLTs (high level group terms), HLT (high level terms) and PTs (preferred terms). Customized SMQs (Novartis MedDRA queries, NMQ) may also be used. A NMQ is a customized group of search terms which defines a medical concept for which there is no official SMQ available or the available SMQ does not completely fit the need. It may include a combination of single terms and/or an existing SMQ, narrow or broad.

For each specified AESI, number and percentage of patients with at least one event of the AESI occurring during on treatment period will be summarized.

Summaries of these AESIs will be provided (specifying grade, SAE, relationship, leading to treatment discontinuation, leading to dose adjustment/interruption, hospitalization, death, requiring immunosuppressive medication etc.). Additional summaries will be provided to report all AESIs, AESIs related to study treatment, all serious AESIs and serious AESIs related to study treatment collected during the on-treatment period and up to 150 days after last administration of PDR001.

A listing of all grouping levels down to the MedDRA preferred terms used to define each AESI will be generated.

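### SAP 2.2.1 splits ORR by irAE occurrence, a post-baseline event tied to time on drug, so that row cannot show homogeneity of treatment effect

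*SAP*

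**What the plan says.** SAP 2.2.1 lists the ORR subgroups for the well-differentiated NET group: cohort, sex, race, PD-L1 expression, age, tumor grade, ECOG status and, last, "Occurrence of at least one immune-related AE (yes, no". It then states: "The objective of the efficacy subgroup analysis is to demonstrate homogeneity of treatment effect in the above subgroups". Output is the ORR and its 95% CI per row, if numbers suffice.

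SAP 2.5.4 sets the condition: "If both criteria for the primary efficacy analysis are met, the primary endpoint of ORR will be summarized for the subgroups specified in" Section 2.2.1. It also describes the purpose more softly: "Efficacy analyses in subgroups will be purely exploratory and are intended to explore the consistency of treatment effect".

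On timing, SAP 2.1.1 defines the on-treatment period for adverse events as "from date of first administration of study treatment to 30 days after date of last actual administration of any study treatment". SAP 2.8.1.1 adds AESI summaries "collected during the on-treatment period and up to 150 days after last administration of PDR001". Section 2.2.1 does not say which window applies to the irAE split. On exposure, Protocol 4.1 states: "Patients will continue to receive the assigned study treatment until disease progression by RECIST 1.1 or as per irRECIST". Neither document gives a landmark, a time-dependent method, an exposure adjustment or a caution for this row.

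**The concern.** A subgroup meant to show homogeneity should be fixed before the outcome can influence it. Here the outcome can influence subgroup membership. Treatment runs to progression, and a confirmed response needs two determinations at least 4 weeks apart on 8-weekly scans, so a scheduled confirmation comes at about week 16 or later. Responders would therefore usually have more time in which an irAE can be recorded. An ever/never split then places relatively more responders in the yes row, whether or not irAEs and response are related.

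If the table is produced, a difference between the two rows could be read as heterogeneity, or as irAEs predicting response, when it may reflect only time on drug. Similar rows would not show homogeneity either.

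**Working it through.** **1. When the table appears.** The plan's figure reproduces: 9/90 = 10.0%, Clopper-Pearson 95% CI 4.7 to 18.1%. The actual full analysis set in this group is 95 (Protocol 1.2.1.2).
- 9/95 = 9.5%, CI 4.4 to 17.2%: excludes 3% but fails the 10% criterion.
- 10/95 = 10.5%, CI 5.2 to 18.5%: meets both.
- Last reported: 7/95 = 7.4%, plus one unconfirmed partial response in the GI cohort. Three more confirmed responders are needed, or two if that one is confirmed.

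**2. Formula under no association.** Let π be the ORR, and let qR and qN be the probabilities of a recorded irAE in responders and non-responders. The irAE hazard per month is the same in both.
- ORR(yes) = π·qR / [π·qR + (1−π)·qN]
- ORR(no) = π·(1−qR) / [π·(1−qR) + (1−π)·(1−qN)]

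The rows are equal if qR = qN. The yes row is higher if qR > qN, that is, if responders are at risk longer.

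**3. Assumptions.** The documents give no irAE rate and no exposure by response.
- π = 10%; irAE hazard 3 to 10% per month, either constant or front-loaded (falling fivefold after month 3).
- Non-responder exposure exponential, mean 6.5 or 8 months (medians 0.693 × 6.5 = 4.5 and 0.693 × 8 = 5.5). These are near the 4.5 and 5.6 month median PFS quoted for another PD-1 antibody in Protocol 1.1.1.
- Responder exposure 4 months plus an exponential of mean 12 (long) or 4 (short).
- Follow-up ends at 14 months: median 5.3 months on 29-Nov-2017 plus 8.3 months to 10-Aug-2018 = 13.6.
- AE window 30 or 150 days after last dose, ended at the cut-off because SAP 2.1 excludes later data.

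**4. One case by hand.** Constant hazard h = 0.05, window w = 30/30.4375 = 0.986 months, cut-off C = 14, long responder exposure, non-responder mean 6.5. For exposure of a plus an exponential of mean m, put d = C − a − w. Then

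1 − q = e^(−h(a+w)) · [1/(1+hm)] · [1 − e^(−(1/m+h)d)] + e^(−d/m) · e^(−hC)

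- Responders (a = 4, m = 12, d = 9.014): 0.7793 × 0.625 × 0.6994 + 0.4718 × 0.4966 = 0.341 + 0.234 = 0.575, so qR = 0.425.
- Non-responders (a = 0, m = 6.5, d = 13.014): 0.9519 × 0.7547 × 0.9296 + 0.1350 × 0.4966 = 0.668 + 0.067 = 0.735, so qN = 0.265.
- ORR(yes) = 0.0425 / (0.0425 + 0.2385) = 0.151.
- ORR(no) = 0.0575 / (0.0575 + 0.6615) = 0.080.
- Ratio 0.151/0.080 = 1.89, with no association built in.

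**5. All settings.** Simulation, 2,000,000 patients per scenario, error about 0.01 in the ratio. The example column uses 5% per month, 30 days and non-responder mean 6.5 months.

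| Hazard | Responder exposure | Example ORR yes / no | Ratio, all scenarios |
|---|---|---|---|
| Constant | Long | 0.151 / 0.080 | 1.29–2.30 |
| Constant | Short | 0.125 / 0.090 | 1.17–1.54 |
| Front-loaded | Long | 0.127 / 0.095 | 1.11–1.39 |
| Front-loaded | Short | 0.114 / 0.097 | 1.06–1.20 |

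**6. Outside the no-association model.** An irAE can lead to interruption, permanent discontinuation or steroids (Protocol 6.3.1.2), and so might prevent a response. If 30% of would-be responders with an irAE before month 3.7 lose their response (an assumption), the front-loaded, short-exposure ratio becomes 0.84 to 0.91. The direction is then reversed.

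**The case against.** The strongest reply is that the SAP has already limited this table. It is called purely exploratory, has no test, and is produced only after success on both criteria and with enough patients per row. The sponsor had also already ended single-agent development in NET. All of this stands and settles the severity. It does not make the row valid: an exploratory label warns about precision and multiplicity, not about a systematic bias, and 2.2.1 still speaks of demonstrating homogeneity.

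Two further points stand in part. Before the primary cut-off, Protocol 6.1.5.1 says "patients treated with PDR001 will be permitted to continue study treatment beyond initial disease progression as per RECIST 1.1", which lengthens non-responder exposure and narrows the gap. And the sizes above rest on borrowed values: the PFS figures come from another antibody in PD-L1-positive patients, include responders, and are not time on drug.

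A reader might infer that the yes row is bound to show the higher ORR. The documents do not support that. It holds in expectation only if responders are on drug longer and irAEs do not themselves cost responses, and with about 10 responders a single table may tie or reverse. A reader might also want a probability that the table will appear. None can be derived: scans after progression (Protocol Appendix 1, section 3.1) or after new antineoplastic therapy (SAP 2.5.1) do not count towards best overall response, and the documents do not say how many non-responders could still respond.

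**Conclusion.** The concern holds and is minor. The irAE row is defined by a post-baseline event whose chance of being recorded grows with time on drug, so it cannot serve the aim stated in SAP 2.2.1. With no true association, and under the assumptions listed, the yes/no ORR ratio would be about 1.06 to 2.3. The size is uncertain, and effects of irAE management could offset or reverse it. The row is uninterpretable as homogeneity in either direction.

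A reader might go further and infer that the primary ORR or the success decision is biased. That does not follow: the split enters neither, and no endpoint, sample size or decision depends on it.

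**What to change.** Delete the irAE item from the efficacy subgroup list in SAP 2.2.1. This is one line and needs no new data; the small loss is a simple irAE-by-response table.

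If the association is wanted, report it in a separate section as descriptive association only:
- define irAEs by the AESI groupings of SAP 2.8.1.1 and state the window;
- treat irAE status as a time-dependent covariate, or fix it at a landmark among patients not yet in response and count only later responses;
- state which assessments count. SAP 2.5.1 uses those before further antineoplastic therapy, while Protocol Appendix 1, section 3.1 by default drops those more than 30 days after the last dose. The two must be reconciled;
- say in advance that the result will be very imprecise.

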2.3 Patient disposition, demographics and other baseline characteristics

The Full Analysis Set (FAS) will be used for all baseline and demographic summaries and listings unless otherwise specified.

Basic demographic and background data

All demographic and baseline disease characteristics data will be summarized and listed. Categorical data (e.g. sex, age groups: <65 and ≥ 65 years, race, ethnicity, ECOG performance status, PD-L1 status) will be summarized by frequency counts and percentages; the number and percentage of patients with missing data will be provided. Continuous data (e.g. age, weight, height, body surface area, body mass index) will be summarized by descriptive statistics (N, mean, median, standard deviation, minimum and maximum).

BMI (kg/m²) will be calculated as $\text{weight}[\text{kg}] / (\text{height}[\text{m}]^2)$ using weight at Baseline.

Diagnosis and extent of cancer

Summary statistics will be tabulated for diagnosis and extent of cancer. This analysis will include the following: primary site of cancer, details of tumor histology/cytology, histological grade, stage at initial diagnosis, time since initial diagnosis, time from initial diagnosis to first recurrence/progression (in months), time since most recent relapse/progression to start of study treatment (in months), stage at time of study entry, presence/absence of target and non-target lesions, number and type of metastatic sites involved.

Note: Presence/absence of target and non-target lesions will be based on the data collected on RECIST target/non-target lesion assessment eCRF pages. Metastatic sites will be based on diagnosis page.

Medical history

Medical history and ongoing conditions, including cancer-related conditions and symptoms entered on (e) CRF will be summarized and listed. The summaries will be presented by primary system organ class (SOC) and preferred term (PT). Medical history and current medical conditions will be coded using the Medical Dictionary for Regulatory Activities (MedDRA) terminology. The MedDRA version used for reporting will be specified in the CSR and as a footnote in the applicable tables/listings.

Other

All data collected at baseline, including child bearing potential [REDACTED] will be listed.

2.3.1 Patient disposition

Enrollment by country and center will be summarized for all screened patients. The number (%) of treated patients included in the FAS will be presented. The number (%) of screened and not-treated patients and the reasons for screening failure will also be displayed. The number (%) of patients in the FAS who are still on treatment, who discontinued the study phases and the reason for discontinuation will be presented.

The following summaries will be provided (with % based on the total number of FAS patients):

- Number (%) of patients who are still on-treatment (based on the ‘End of Treatment Phase’ page not completed);
- Number (%) of patients who discontinued the study treatment phase (based on the ‘End of Treatment Phase’ page)
- Primary reason for study treatment phase discontinuation (based on the ‘End of Treatment Phase’ page)
- Number (%) of patients who have entered the post-treatment follow-up (based on the ‘End of Treatment Phase’ page);
- Number (%) of patients who have discontinued from the post-treatment follow-up (based on the ‘End of Post-treatment follow-up page’);
- Reasons for discontinuation from the post-treatment follow-up (based on ‘End of Post-treatment follow-up page’);
- Number (%) of patients who have entered the survival follow-up (based on the ‘End of Treatment Phase’ or ‘End of Post-treatment follow-up’ page).

Protocol deviations

The number (%) of patients in the FAS with any protocol deviation will be tabulated by deviation category (as specified in the study specification document) for all patients. All protocol deviations will be listed.

Analysis sets

The number (%) of patients in each analysis set (defined in [Section 2.2](#)) will be summarized.

